#### 6.4 Management of Other Clinically Significant AEs (not specifically addressed above)

##### General Management Guidelines

Observation	Action
AE resolves promptly with supportive care	Maintain dose level
Grade 3 or higher non-hematologic related to sunitinib despite maximum supportive care for $\leq$ 48 hours.	Hold sunitinib until resolution to $\leq$ grade 2, then reduce by one dose level
AE does not resolve to grade 2 or below after 2 weeks off sunitinib	Remove patient from study
Recurrent grade 3 or higher non-hematologic on the lowest dose level ( i.e. , 25 mg daily).	Remove patient from study

In general, patients requiring sunitinib malate treatment to be held for greater than 2 weeks are to be discontinued from the study; however, in the rare event that a patient requires sunitinib malate treatment to be held for greater than 2 weeks in order to receive treatment for an unrelated concurrent medical condition, the patient may be permitted to continue sunitinib malate treatment on study following treatment of their concurrent medical condition if specific requirements are met and if approved by the CTEP drug monitor. For a patient where it is evident that the patient has benefitted, and continues to benefit from treatment (*i.e.*, a confirmed partial response or extended stable disease has been determined according to RECIST); the re-start of sunitinib malate treatment following an extended sunitinib malate treatment holiday may be permissible if the investigator determines that:

- the patient is of sufficient health to continue following the intervention for the patient's concurrent medical condition
- continued sunitinib malate treatment would not subject the patient to undue harm
- there exists the possibility of the patient to derive continued benefit from further sunitinib malate treatment.

The investigator will assess the patient's disease and the potential benefit of continued sunitinib

treatment before and after the extended drug holiday.

## 7. ADVERSE EVENTS: LIST AND REPORTING REQUIREMENTS

Adverse event (AE) monitoring and reporting is a routine part of every clinical trial. The following list of AEs (Section 7.1) and the characteristics of an observed AE (Section 7.2) will determine whether the event requires expedited (via AERS) reporting **in addition** to routine (via CDUS) reporting. See the company's prescribing information regarding hepatotoxicity at [www.sutent.com](http://www.sutent.com).

### 7.1 Comprehensive Adverse Events and Potential Risks List (CAEPR) for Sunitinib Malate (NSC 736511)

The Comprehensive Adverse Events and Potential Risks list (CAEPR) provides a single list of reported and/or potential adverse events (AE) associated with an agent using a uniform presentation of events by body system. In addition to the comprehensive list, a subset, the Specific Protocol Exceptions to Expedited Reporting (SPEER), appears in a separate column and is identified with bold and italicized text. This subset of AEs (SPEER) is a list of events that are protocol specific exceptions to expedited reporting to NCI (except as noted below). Refer to the 'CTEP, NCI Guidelines: Adverse Event Reporting Requirements' [http://ctep.cancer.gov/protocolDevelopment/electronic\\_applications/docs/aeguidelines.pdf](http://ctep.cancer.gov/protocolDevelopment/electronic_applications/docs/aeguidelines.pdf) for further clarification. Frequency is provided based on 7115 patients. Below is the CAEPR for Sunitinib malate (SU011248 L-malate).

**NOTE:** Report AEs on the SPEER **ONLY IF** they exceed the grade noted in parentheses next to the AE in the SPEER. If this CAEPR is part of a combination protocol using multiple investigational agents and has an AE listed on different SPEERs, use the lower of the grades to determine if expedited reporting is required.

Version 2.12, January 14, 2016

Adverse Events with Possible Relationship to Sunitinib malate (SU011248 L-malate) (CTCAE 4.0 Term) [n= 7115]			Specific Protocol Exceptions to Expedited Reporting (SPEER)
Likely (>20%)	Less Likely (<=20%)	Rare but Serious (<3%)	
BLOOD AND LYMPHATIC SYSTEM DISORDERS			
	Anemia		Anemia (Gr 3)
		Hemolytic uremic syndrome	
		Thrombotic thrombocytopenic purpura	
CARDIAC DISORDERS			
		Cardiac disorders - Other (cardiomyopathy)	
		Heart failure	
		Left ventricular systolic dysfunction	
		Myocardial infarction	
ENDOCRINE DISORDERS			
		Endocrine disorders - Other (thyroiditis)	
		Hyperthyroidism	
	Hypothyroidism		Hypothyroidism (Gr 2)
EYE DISORDERS			
		Eye disorders - Other (macular edema)	Eye disorders - Other (macular edema) (Gr 2)

Adverse Events with Possible Relationship to Sunitinib malate (SU011248 L-malate) (CTCAE 4.0 Term) [n= 7115]			Specific Protocol Exceptions to Expedited Reporting (SPEER)
Likely (>20%)	Less Likely (<=20%)	Rare but Serious (<3%)	
		Eye disorders - Other (vision deterioration)	Eye disorders - Other (vision deterioration) (Gr 2)
	Papilledema		Papilledema (Gr 2)
GASTROINTESTINAL DISORDERS			
	Abdominal distension		Abdominal distension (Gr 2)
Abdominal pain			Abdominal pain (Gr 3)
Anal mucositis			Anal mucositis (Gr 2)
Constipation			Constipation (Gr 2)
Diarrhea			Diarrhea (Gr 3)
	Dry mouth		Dry mouth (Gr 2)
Dyspepsia			Dyspepsia (Gr 2)
		Esophagitis	
	Flatulence		Flatulence (Gr 2)
	Gastritis		Gastritis (Gr 2)
	Gastroesophageal reflux disease		
		Gastrointestinal perforation 	
Mucositis oral			Mucositis oral (Gr 3)
Nausea			Nausea (Gr 3)
	Oral pain		Oral pain (Gr 2)
		Pancreatitis	
Rectal mucositis			Rectal mucositis (Gr 2)
Small intestinal mucositis			Small intestinal mucositis (Gr 2)
Vomiting			Vomiting (Gr 3)
GENERAL DISORDERS AND ADMINISTRATION SITE CONDITIONS			
	Chills		Chills (Gr 2)
	Edema limbs		Edema limbs (Gr 2)
Fatigue			Fatigue (Gr 3)
	Fever		Fever (Gr 2)
	Non-cardiac chest pain		Non-cardiac chest pain (Gr 2)
HEPATOBILIARY DISORDERS			
		Cholecystitis	
		Hepatic failure	
IMMUNE SYSTEM DISORDERS			
		Allergic reaction 	
INFECTIONS AND INFESTATIONS			
		Infection and infestations - Other (necrotizing fasciitis)	
INJURY, POISONING AND PROCEDURAL COMPLICATIONS			
		Wound complication	
INVESTIGATIONS			
	Alanine aminotransferase increased		Alanine aminotransferase increased (Gr 3)
	Alkaline phosphatase increased		Alkaline phosphatase increased (Gr 2)
	Aspartate aminotransferase increased		Aspartate aminotransferase increased (Gr 3)
	Blood bilirubin increased		Blood bilirubin increased (Gr 2)
	CPK increased		

Adverse Events with Possible Relationship to Sunitinib malate (SU011248 L-malate) (CTCAE 4.0 Term) [n= 7115]			Specific Protocol Exceptions to Expedited Reporting (SPEER)
Likely (>20%)	Less Likely (<=20%)	Rare but Serious (<3%)	
	Creatinine increased		Creatinine increased (Gr 3)
		Electrocardiogram QT corrected interval prolonged	
	Lipase increased		Lipase increased (Gr 4)
	Lymphocyte count decreased		Lymphocyte count decreased (Gr 2)
	Neutrophil count decreased		Neutrophil count decreased (Gr 4)
	Platelet count decreased		Platelet count decreased (Gr 4)
	Serum amylase increased		Serum amylase increased (Gr 2)
	Weight loss		Weight loss (Gr 2)
	White blood cell decreased		White blood cell decreased (Gr 3)
METABOLISM AND NUTRITION DISORDERS			
Anorexia			Anorexia (Gr 3)
	Dehydration		Dehydration (Gr 3)
	Hyperuricemia		Hyperuricemia (Gr 2)
	Hypoalbuminemia		Hypoalbuminemia (Gr 2)
		Hypoglycemia	
	Hypophosphatemia		Hypophosphatemia (Gr 2)
		Tumor lysis syndrome	
MUSCULOSKELETAL AND CONNECTIVE TISSUE DISORDERS			
	Arthralgia		Arthralgia (Gr 2)
	Back pain		Back pain (Gr 2)
		Musculoskeletal and connective tissue disorder - Other (rhabdomyolysis)	
	Myalgia		Myalgia (Gr 2)
		Osteonecrosis of jaw	
	Pain in extremity		Pain in extremity (Gr 2)
NERVOUS SYSTEM DISORDERS			
	Dizziness		
Dysgeusia			Dysgeusia (Gr 2)
	Headache		Headache (Gr 3)
		Leukoencephalopathy	
		Nervous system disorders - Other (cerebral infarction)	
	Paresthesia		
		Reversible posterior leukoencephalopathy syndrome	
		Transient ischemic attacks	
PSYCHIATRIC DISORDERS			
	Depression		
	Insomnia		Insomnia (Gr 2)
RENAL AND URINARY DISORDERS			
		Acute kidney injury	
		Proteinuria	
		Renal and urinary disorders - Other (nephrotic syndrome)	
RESPIRATORY, THORACIC AND MEDIASTINAL DISORDERS			
	Cough		Cough (Gr 2)

Adverse Events with Possible Relationship to Sunitinib malate (SU011248 L-malate) (CTCAE 4.0 Term) [n= 7115]			Specific Protocol Exceptions to Expedited Reporting (SPEER)
Likely (>20%)	Less Likely (<=20%)	Rare but Serious (<3%)	
	Dyspnea		Dyspnea (Gr 3)
	Epistaxis		Epistaxis Gr 2)
Laryngeal mucositis			Laryngeal mucositis (Gr 2)
Pharyngeal mucositis			Pharyngeal mucositis (Gr 2)
Tracheal mucositis			Tracheal mucositis (Gr 2)
SKIN AND SUBCUTANEOUS TISSUE DISORDERS			
	Alopecia		Alopecia (Gr 2)
	Dry skin		Dry skin (Gr 2)
Palmar-plantar erythrodysesthesia syndrome		Erythema multiforme	Palmar-plantar erythrodysesthesia syndrome (Gr 3)
	Pruritus		
	Rash maculo-papular		Rash maculo-papular (Gr 3)
	Skin and subcutaneous tissue disorders - Other (hair color change)		Skin and subcutaneous tissue disorders - Other (hair color change) (Gr 2)
		Skin and subcutaneous tissue disorders - Other (pyoderma gangrenosum)	
	Skin hypopigmentation		Skin hypopigmentation (Gr 2)
		Stevens-Johnson syndrome	
		Toxic epidermal necrolysis	
VASCULAR DISORDERS			
	Hypertension		Hypertension (Gr 3)
	Vascular disorders - Other (hemorrhage) 		

This table will be updated as the toxicity profile of the agent is revised. Updates will be distributed to all Principal Investigators at the time of revision. The current version can be obtained by contacting [[contact]](mailto:[contact]). Your name, the name of the investigator, the protocol and the agent should be included in the e-mail.

Gastrointestinal perforation includes Colonic perforation, Duodenal perforation, Esophageal perforation, Gastric perforation, Ileal perforation, Jejunal perforation, Rectal perforation, and Small intestinal perforation under the GASTROINTESTINAL DISORDERS SOC.

Allergic reactions observed include anaphylaxis and angioedema.

The majority of hemorrhage events were mild. Major events, defined as symptomatic bleeding in a critical area or organ (e.g., eye, GI tract, GU system, respiratory tract, nervous system [including fatal intracranial hemorrhage, and cerebrovascular accident], and tumor site) have been reported.

**Adverse events reported on Sunitinib malate (SU011248 L-malate) trials, but for which there is insufficient evidence to suggest that there was a reasonable possibility that Sunitinib malate (SU011248 L-malate) caused the adverse event:**

**BLOOD AND LYMPHATIC SYSTEM DISORDERS** - Febrile neutropenia

**CARDIAC DISORDERS** - Atrial fibrillation; Cardiac arrest; Pericardial effusion

**GASTROINTESTINAL DISORDERS** - Ascites; Dysphagia; Gastrointestinal disorders - Other (enteritis); Hemorrhoids; Ileus; Small intestinal obstruction

**GENERAL DISORDERS AND ADMINISTRATION SITE CONDITIONS** - Pain

**INVESTIGATIONS** - GGT increased; INR increased

**METABOLISM AND NUTRITION DISORDERS** - Hypercalcemia; Hyperglycemia; Hyperkalemia; Hypocalcemia; Hypokalemia; Hyponatremia

**MUSCULOSKELETAL AND CONNECTIVE TISSUE DISORDERS** - Bone pain

**NERVOUS SYSTEM DISORDERS** - Cognitive disturbance; Nervous system disorders - Other (spinal cord compression); Peripheral sensory neuropathy; Seizure; Syncope

**PSYCHIATRIC DISORDERS** - Anxiety; Confusion

**RENAL AND URINARY DISORDERS** - Hematuria; Urinary retention

**REPRODUCTIVE SYSTEMS AND BREAST DISORDERS** - Hematosalpinx

**RESPIRATORY, THORACIC AND MEDIASTINAL DISORDERS** - Pharyngolaryngeal pain; Pleural effusion; Pneumothorax

**VASCULAR DISORDERS** - Flushing; Hypotension; Thromboembolic event

**Note:** Sunitinib malate (SU011248 L-malate) in combination with other agents could cause an exacerbation of any adverse event currently known to be caused by the other agent, or the combination may result in events never previously associated with either agent.

## 7.2 Adverse Event Characteristics

- **CTCAE term (AE description) and grade:** The descriptions and grading scales found in the revised NCI Common Terminology Criteria for Adverse Events (CTCAE) version 3.0 will be utilized for AE reporting. All appropriate treatment areas should have access to a copy of the CTCAE version 3.0. A copy of the CTCAE version 3.0 can be downloaded from the CTEP web site (<http://ctep.cancer.gov>). Please consult the CTEP [mapping document of CTCAE version 3.0 to CTCAE version 4.0](#) when determining expectedness and expedited adverse event reporting.
- **“Expectedness”:** AEs can be ‘Unexpected’ or ‘Expected’ (see Section 7.1 above) for expedited reporting purposes only. ‘Expected’ AEs (the SPEER) are ***bold and italicized*** in the CAEPR (Section 7.1).
- **Attribution** of the AE:
  - Definite – The AE is *clearly related* to the study treatment.
  - Probable – The AE is *likely related* to the study treatment.
  - Possible – The AE *may be related* to the study treatment.
  - Unlikely – The AE is *doubtfully related* to the study treatment.
  - Unrelated – The AE is *clearly NOT related* to the study treatment.

## 7.3 Expedited Adverse Event Reporting

7.3.1 Expedited AE reporting for this study must use CTEP-AERS (CTEP Adverse Event Reporting System), accessed via the CTEP home page (<http://ctep.cancer.gov>). The reporting procedures to be followed are presented in the “CTEP, NCI Guidelines: Adverse Event Reporting Requirements” which can be downloaded from the CTEP home page (<http://ctep.cancer.gov>). These requirements are briefly outlined in the table below (Section 7.3.3).

In the rare event when Internet connectivity is disrupted a 24-hour notification is to be made to NCI by telephone at: [contact], or [contact] for CIP studies. An electronic report MUST be submitted immediately upon re-establishment of internet connection

7.3.2 CTEP-AERS is programmed for automatic electronic distribution of reports to the following individuals: Study Coordinator of the Lead Organization, Principal Investigator, and the local treating physician. CTEP-AERS provides a copy feature for other e-mail recipients.

### 7.3.3 Expedited Reporting Guidelines

CTEP-AERS Reporting Requirements for Adverse Events that occur within 30 Days of the Last Dose of the Investigational Agent on Phase 2 and 3 Trials

Phase 2 and 3 Trials									
	Grade 1	Grade 2	Grade 2	Grade 3		Grade 3		Grades 4 & 5 	Grades 4 & 5 
	Unexpected and Expected	Unex-pected	Expected	Unexpected with Hospitalization	without Hospitalization	Expected with Hospitalization	without Hospitalization	Unex-pected	Expected
Unrelated Unlikely	Not Required	Not Required	Not Required	10 Calendar Days	Not Required	10 Calendar Days	Not Required	10 Calendar Days	10 Calendar Days
Possible Probable Definite	Not Required	10 Calendar Days	Not Required	10 Calendar Days	10 Calendar Days	10 Calendar Days	Not Required	24-Hour; 5 Calendar Days	10 Calendar Days

 Adverse events with attribution of possible, probable, or definite that occur greater than 30 days after the last dose of treatment with an agent under a CTEP IND require reporting as follows:

CTEP-AERS 24-hour notification followed by complete report within 5 calendar days for:

- Grade 4 and Grade 5 unexpected events

CTEP-AERS 10 calendar day report:

- Grade 3 unexpected events with hospitalization or prolongation of hospitalization
- Grade 5 expected events

 Although a CTEP-AERS 24-hour notification is not required for death clearly related to progressive disease, a full report is required as outlined in the table.

December 15, 2004

**Note: All deaths on study require both routine and expedited reporting regardless of causality. Attribution to treatment or other cause must be provided.**

- Expedited AE reporting timelines defined:

- “24 hours; 5 calendar days” – The investigator must initially report the AE via CTEP-AERS within 24 hours of learning of the event followed by a complete CTEP-AERS report within 5 calendar days of the initial 24-hour report.
- “10 calendar days” - A complete CTEP-AERS report on the AE must be submitted within 10 calendar days of the investigator learning of the event.
- Any medical event equivalent to CTCAE grade 3, 4, or 5 that precipitates hospitalization (or prolongation of existing hospitalization) must be reported regardless of attribution and designation as expected or unexpected with the exception of any events identified as protocol-specific expedited adverse event reporting exclusions.
- Any event that results in persistent or significant disabilities/incapacities, congenital anomalies, or birth defects must be reported via CTEP-AERS if the event occurs following treatment with an agent under a CTEP IND.
- Use the NCI protocol number and the protocol-specific patient ID assigned during trial registration on all reports.

#### 7.4 Routine Adverse Event Reporting

All Adverse Events **must** be reported in routine study data submissions. **AEs reported through CTEP-AERS must also be reported in routine study data submissions.**

#### 7.5 Secondary AML/MDS

All secondary malignancies that occur following treatment with an agent under an NCI IND/IDE must be reported via CTEP-AERS. CTCAE v4.0 has three options available to describe treatment-related events:

- Leukemia secondary to oncology chemotherapy,
- Myelodysplastic syndrome,
- Treatment related secondary malignancy.

If you are reporting in CTCAE v3.0, the event can be reported as: “Secondary malignancy-Other (Specify)”.

### 8. PHARMACEUTICAL INFORMATION

A list of the adverse events and potential risks associated with **sunitinib malate** administered in this study can be found in Section 7.1.

#### Sunitinib malate (NSC 736511)

**Chemical Name:** 5-(5-fluoro-2-oxo-1,2-dihydro-indol-(3Z)-ylidenemethyl)-2,4-dimethyl-1H-pyrrole-3-carboxylic acid(2-diethylamino-ethyl)-amide; compound with (S)-2-hydroxy-succinic acid.

**Other names:** SU011248 L-Malate salt; SU010398; PHA-290940AD; Sutent; SU011248

**Classification:** Receptor tyrosine kinase (RTK) inhibitor

**Molecular formula:** C22H27FN4O2.C4H6O5      **M.W.:** 532.57 Daltons

**Physical description:** Yellow to orange powder

**CAS registry number:** 341031-54-7

**Aqueous solubility:**

Solvent	Solubility (mg/mL)
0.1 M HCl	59.1
pH 4.5 buffer	25.4
pH 7.5 buffer	37.8
In water	4.9

**Solubility in various solvents:**

Solvent	Solubility (mg/mL)
Tetrahydrofuran	0.2
1-Butano:Water (80/20 v:v)	1.0
N, N-Dimethylacetamide	3.0

**Mode of Action:** Sunitinib malate is a receptor tyrosine kinase inhibitor involved in tumor proliferation and angiogenesis, specifically inhibiting platelet derived growth factor receptor, vascular endothelial growth factor receptor, stem cell factor receptor, Fms-like tyrosine kinase-3 receptor, and *ret* proto-oncogene.

**How Supplied:** Sunitinib malate is supplied by Pfizer and distributed by DCTD/NCI as 12.5 mg, 25 mg, and 50 mg capsules with mannitol, croscarmellose sodium, povidone, and magnesium stearate. Each opaque plastic bottle contains 30 capsules.

Capsule strength	Description
12.5 mg	Swedish Orange, Size 4 hard gelatin capsule
25 mg	Swedish Orange/Caramel, Size 3 hard gelatin capsule.
50 mg	Caramel, Size 2 hard gelatin capsule

**Storage:** Store at controlled room temperature (15 to 30^0 C), and protect from light.

**Stability:** Shelf-life studies for sunitinib capsules are ongoing.

**Route of Administration:** Oral. Sunitinib malate may be administered without regard to meals.

**Potential Drug Interaction:** Sunitinib malate is metabolized primarily by liver enzymes, particularly CYP3A4. CYP3A4 inducers (e.g., rifampin,

dexamethasone) and CYP3A4 inhibitors (e.g., grapefruit juice, ketoconazole) should be avoided, if possible. Rifampin lowers sunitinib malate Cmax concentration by more than 2-fold. Ketoconazole increases sunitinib malate Cmax by 1.6 fold. Dose reduction with the CYP3A4 inhibitors is recommended, based on clinical symptoms.

Concomitant treatment with dysrhythmic drugs, *i.e.*, terfenadine, quinidine, procainamide, sotalol, probucol, bepridil, haloperidol, risperidone, and indapamide, is not recommended.

**Patient Care Implications:** A yellow discoloration of the skin area may result following direct contact with the capsules. Wash the exposed area with soap and water immediately.

**Availability:** Sunitinib malate is an investigational agent supplied to investigators by the Division of Cancer Treatment and Diagnosis (DCTD), NCI. Sunitinib malate is provided to the NCI under a Collaborative Agreement between Pfizer and the DCTD, NCI (see Section 11.3).

**Agent Ordering:** NCI-supplied agents may be requested by the Principal Investigator (or their authorized designees) at each participating institution. Pharmaceutical Management Branch (PMB) policy requires that the agent be shipped directly to the institution where the patient is to be treated. PMB does not permit the transfer of agents between institutions (unless prior approval from PMB is obtained).

Active CTEP-registered investigators and investigator-designated shipping designees and ordering designees can submit agent requests through the PMB Online Agent Order Processing (OAOP) application <https://eapps-ctep.nci.nih.gov/OAOP/pages/login.jspx>. Access to OAOP requires the establishment of a CTEP Identity and Access Management (IAM) account <https://eapps-ctep.nci.nih.gov/jam/> and the maintenance of an “active” account status and a “current” password. For questions about drug orders, transfers, returns, or accountability, call [contact] Monday through Friday between 8:30 am and 4:30 pm (ET) or email [contact] anytime.

**Agent Accountability:** The Investigator, or a responsible party designated by the investigator, must maintain a careful record of the inventory and disposition of all agents received from DCTD using the

NCI Drug Accountability Record Form. *See the CTEP web site for Policy and Guidelines for Accountability and Storage of Investigational Drugs (<http://ctep.cancer.gov/requisition/storage.html>), or call the PMB at [contact].*

## 9. STUDY CALENDAR

Baseline evaluations are to be conducted within 1 week prior to administration of protocol therapy. Tumor imaging studies must be done  $\square$  4 weeks prior to the start of therapy. In the event that the patient's condition is deteriorating, laboratory evaluations should be repeated within 48 hours prior to initiation of the next cycle of therapy.

	Pre-Study	Wk 1	Wk 2	Wk 3	Wk 4	Wk 5	Wk 6	Wk 7	Wk 8	Wk 9	Wk 10	Wk 11	Wk 12	Wk 13	Off Study
Sunitinib		X	X	X	X			X	X	X	X				
Informed consent	X														
Demographics	X														
Medical history	X														
Concurrent meds	X	X-----X													
Physical exam	X	X		X		X		X					X	X	
Vital signs	X	X		X		X		X					X	X	
Height	X														
Weight	X	X		X		X		X					X	X	
Performance status	X	X		X		X		X					X	X	
CBC w/diff, plts	X								X				X	X	
Serum chemistry a	X	X							X				X	X	
Blood pressure measurement b	X	X	X	X	X	X	X	X					X	X	
Electrocardiogram c	X														
Echocardiogram or MUGA d (as indicated)	X												X		
Adverse event evaluation		X-----X												X	
Tumor measurements	X	Tumor measurements are repeated every 2 cycles . f Documentation (radiologic) must be provided for patients removed from study for progressive disease.													X
Radiologic evaluation	X	Radiologic measurements should be performed every 2 cycles . f													X
B-HCG	X e														

a: Albumin, alkaline phosphatase, amylase, total bilirubin, bicarbonate, BUN, calcium, chloride, creatinine, glucose, LDH, lipase, phosphate, potassium, total protein, SGOT[AST], SGPT[ALT], sodium, magnesium, TSH, T3 & T4. LFTs should be obtained at any time when they are clinically indicated

b: Blood pressure measurement may be performed more frequently as dictated by clinical observations.

c: All patients must have ECG at baseline. Follow-up ECGs as clinically indicated

d: All patients must have echo or MUGA at baseline. Echo / MUGA must be repeated every other cycle for high-risk patients only (see sections 3.1.9 and 5.1)

e: Serum pregnancy test (women of childbearing potential).

f: In the rare event that sunitinib treatment is discontinued for an extended period to permit treatment of an unrelated concurrent medical condition radiologic evaluation and tumor measurements are to be repeated prior to re-initiation of treatment if deemed necessary by the investigator.

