### 6.3 Other Hematologic and Non-Hematologic Adverse Events

Event	AE Grade or Observation	Dose modification
Neutropenia	Grades 1 and 2	Maintain dose
	Grade 3 *	Hold sunitinib until $\leq$ grade 2, then resume at same dose level
	Grade 4	Hold sunitinib until $\leq$ grade 2, then reduce 1 dose level and resume treatment
Thrombocytopenia	Grades 1 and 2	Maintain dose
	Grade 3 *	Hold sunitinib until $\leq$ grade 2, then resume at same dose level
	Grade 4	Hold sunitinib until $\leq$ grade 2, then reduce 1 dose level and resume treatment
Fatigue (lethargy, malaise, asthenia)	Grades 1 and 2	Maintain dose
	Grade 3 *	Hold sunitinib until $\leq$ grade 2, then reduce 1 dose level and resume treatment
	Grade 4	Hold sunitinib until $\leq$ grade 2, then reduce 1 dose level and resume treatment
QTc Prolongation	>450 but $<$ 550 msec	
 
Review patient's concomitant medications for QT interval-prolonging agents. Correct any electrolyte abnormalities.
 
Continue sunitinib at current dose level.
 

	$\geq$ 550 msec	
 
Stop sunitinib and any other QT-interval prolonging agents immediately. Correct any electrolyte abnormalities, then                     
 
If there is a plausible explanation for AE other than sunitinib treatment, resume sunitinib at current dose level.
 
If sunitinib may have contributed to the AE:                             
 
Reduce 2 dose levels and restart sunitinib.
 
If QTc remains <math><500</math> msec after 14 days at reduced dose, increase one dose level and continue sunitinib.
 
 
 
 
 
 
If QTc remains <math><500</math> msec after 14 days, original dose of sunitinib may be resumed.

Hand-foot syndrome	Grades 1 and 2	Maintain dose
	Grade 3	Hold sunitinib until $\leq$ grade 1, then reduce 1 dose level
	Grade 4	Discontinue treatment
Serum lipase /	Grades 1 and	Maintain dose

amylase	2	
	Grades 3 and 4	Hold sunitinib until $\leq$ grade 1, then reduce 1 dose level
ALT / AST / Bilirubin	$\geq$ Grade 3	Sunitinib should be dose delayed, may be re-administered when levels of ALT / AST / bilirubin is $\leq$ grade 2. Sunitinib should NOT be re-administered if subjects develop $\geq$ grade 3 hepatic failure (CTCAEv4 definition).

- **Recurrent grade 3 events require dose reduction.**

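### As the Section 9 calendar reads, cycle 1 has no scheduled blood count and no chemistry after Wk 1, although Section 6.3 doses on both: check the table, then add draws at Wk 3 and Wk 5

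*Combined protocol and SAP*

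**What the plan says.** The Section 9 calendar has one row for blood counts, "CBC w/diff, plts", and one for serum chemistry. Footnote a lists lipase, amylase, bilirubin, AST and ALT within the chemistry panel. On baseline timing, Section 9 says: "Baseline evaluations are to be conducted within 1 week prior to administration of protocol therapy".

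The footnotes deal unevenly with tests between marks:
- footnote a: "LFTs should be obtained at any time when they are clinically indicated"
- footnote b: "Blood pressure measurement may be performed more frequently as dictated by clinical observations"
- footnote c: "Follow-up ECGs as clinically indicated"

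No footnote does the same for CBC, lipase or amylase. For a patient whose condition is deteriorating, the introduction to Section 9 adds that "laboratory evaluations should be repeated within 48 hours prior to initiation of the next cycle of therapy".

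Section 6.3 makes dosing depend on these results. A first grade 3 neutropenia or thrombocytopenia means a hold and a return at the same dose; grade 4 means a hold and one level down. Grade 3 or 4 lipase or amylase also means a hold and one level down. For liver tests of grade 3 or above, "Sunitinib should be dose delayed, may be re-administered when levels of ALT / AST / bilirubin is" grade 2 or lower. The section closes with "Recurrent grade 3 events require dose reduction". Section 2.2 (Safety Profile) names hematologic events and lipase elevations, with fatigue, as the leading grade 3-4 toxicities across populations.

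**The concern.** A rule that holds or reduces the dose by laboratory grade works only if the laboratory value is measured. Symptoms will prompt some testing, but cytopenias can be silent, and Section 2.2 itself reports lipase rises without symptoms. If nothing is scheduled during cycle 1 dosing beyond a Wk 1 chemistry panel, two things are at stake.

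- **Patient safety.** A patient with an unnoticed grade 3 or 4 value could stay on 50 mg when Section 6.3 would have stopped it. The recurrence rule also cannot act on a second event if the first was never seen.
- **Toxicity data.** Toxicity is a secondary objective (Section 1.2), and Section 12.3 plans tables of grade 3 or higher events. Those tables could be too low for laboratory events in cycle 1, and uneven across sites if some investigators draw blood on their own initiative.

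**Working it through.** **1. Column count.** The calendar header has a label cell and 15 time points, so 16 cells. Each row below also has 16 cells.

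| Row | Marked at |
|---|---|
| Sunitinib | Wk 1-4, 7-10 |
| Physical exam | Pre-Study, Wk 1, 3, 5, 7, 12, 13 |
| Blood pressure | Pre-Study, Wk 1-7, 12, 13 |
| CBC | Pre-Study, Wk 8, 12, 13 |
| Serum chemistry | Pre-Study, Wk 1, 8, 12, 13 |

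**2. Cycle boundaries.** Section 5.1 gives 4 weeks on drug and 2 off, so a cycle is 4 + 2 = 6 weeks. Cycle 1 is Wk 1-6, cycle 2 is Wk 7-12, and cycle 3 starts at Wk 13. The sunitinib row agrees.

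**3. Scheduled tests in cycle 1.** CBC: 0. Chemistry: 1, at Wk 1. The baseline CBC precedes treatment. No other section of the supplied document schedules either test in cycle 1.

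**4. Does a displaced table change this?** There are two signs of displacement. Wk 8 is not a visit week in the physical exam, vital signs, weight or performance status rows. The visit rows also end at Wk 12 and Wk 13 with Off Study empty, whereas the two tumor assessment rows do reach Off Study. The first sign suggests a mark one column too far right, the second marks one column too far left, so no single shift explains both. Moving the Wk 8 mark by one column:
- 8 - 1 = Wk 7, day 1 week of cycle 2;
- 8 + 1 = Wk 9, inside cycle 2.

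To fall in cycle 1 it would have to move at least 8 - 6 = 2 columns left. Correcting both signs (Wk 8 to Wk 7; Wk 12 and 13 to Wk 13 and Off Study) gives a tidy schedule at the start of each cycle, still with nothing between Wk 1 and Wk 7. The conclusion therefore survives a one-column error. It does not survive marks lost altogether from these two rows.

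**5. Would a Wk 7 sample stand in for one taken on drug?** Section 2.2 gives terminal half-lives of about 40 h for sunitinib and 80 h for its active metabolite. Two weeks off drug is 14 x 24 = 336 h, or 336/40 = 8.4 and 336/80 = 4.2 half-lives. The fractions left are 0.5^8.4, about 0.3%, and 0.5^4.2, about 5%. A Wk 7 sample is close to an off-drug sample and may miss an abnormality that arose during dosing and recovered. This describes exposure; the documents give no recovery times for counts or lipase.

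**6. Rules against scheduled measurements in cycle 1.**

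| Section 6 rule | Scheduled in cycle 1 | Test between marks provided for |
|---|---|---|
| Neutrophils, platelets (6.3) | none | no |
| Lipase, amylase (6.3) | Wk 1 only | no |
| ALT/AST, bilirubin (6.3) | Wk 1 only | yes, footnote a |
| QTc (6.3) | none | yes, footnote c |
| Blood pressure (6.1) | weekly | yes, footnote b |

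**7. Effect of adding Wk 3 and Wk 5.** CBCs in cycle 1: 0 + 2 = 2. Chemistry samples: 1 + 2 = 3. At the maximum of 30 patients (Section 12.2), this is at most 30 x 2 = 60 extra samples of each type.

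**8. Statistical design.** The Section 12.1 figures reproduce. The chance of stopping early at a 5% response rate is 0.95^15 = 0.4633, and expected N is 15 + 15 x (1 - 0.4633) = 23.05. The exact two-stage binomial calculation gives type I error 0.0582 and power 0.8649. None of these uses a laboratory value, so none changes.

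**The case against.** The strongest objection is that the evidence is a damaged table. A broken table is not an error in the plan. The two rows at issue are the ones with a mark where no visit exists, and CBC differs from chemistry only by the missing Wk 1 mark, which would fit a mark that dropped out. This stands in full as a condition: the first step is to look at the source page. It does not dispose of the point, because the left part of the table (dosing at Wk 1-4 and 7-10, visits at Wk 1, 3, 5 and 7) reads coherently.

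Second, the calendar is not the whole of monitoring. Visits are marked at Wk 1, 3 and 5, adverse event evaluation is continuous, Section 5.2.2 calls for prompt work-up of neutropenic fever or infection, and Appendix H has bloodwork sent in with the case report forms. Nothing stops an investigator drawing blood at a marked visit. This narrows the gap to asymptomatic cytopenias and lipase or amylase rises. For liver tests, footnote a already gives partial cover.

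Third, sampling frequency is partly preference. Section 2.2 regards 50 mg on the 4/2 schedule as well tolerated, and a first grade 3 cytopenia brings the patient back at the same dose. That is fair, and it is why no draw during dosing is asked for in later cycles: none of those visits is marked, and the documents do not show the need. It is weaker for grade 4 counts and for grade 3-4 lipase or amylase, where Section 6.3 requires a reduction.

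**Conclusion.** This is a cheap safety improvement, conditional on the source table. If the two rows are as they read here, no blood count is scheduled in cycle 1 and no chemistry after Wk 1 until cycle 2. The Section 6.3 rules for neutrophils, platelets and lipase/amylase then rely on unscheduled or symptom-prompted tests throughout most or all of cycle 1 dosing. If the source shows draws at Wk 3 and Wk 5, the point falls away.

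The size is unknown: the documents give no rate of asymptomatic grade 3-4 laboratory events in cycle 1. Response rate, sample size and error rates are unaffected.

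A reader might infer more than this, and the documents do not support it:
- *That the trial left laboratory safety unmonitored in cycle 1.* The calendar does not list all monitoring, and marked visits allow blood to be drawn.
- *That the toxicity tables are materially too low, or that patients were harmed.* Neither can be shown without an event rate.
- *That the gap can be stated in days.* The column positions are too uncertain for that.
- *That the liver-test rules have no support.* Footnote a provides for unscheduled liver tests.

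The documents do not state accrual status. If patients have already been treated under this calendar, the check still matters for reading the grade 3 or higher tables.

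**What to change.** First compare the CBC and serum chemistry rows of Section 9 with the source PDF. If they are confirmed:
- add CBC with differential and platelets, together with lipase, amylase, ALT/AST and bilirubin, at the Wk 3 and Wk 5 visits already marked in cycle 1;
- add a footnote allowing CBC, lipase and amylase at any time when clinically indicated, to match the provision for liver tests.

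The scheduled draws are the essential part, since a footnote tied to clinical indication will not find a silent event. The cost is a calendar amendment and two extra routine blood draws per patient in cycle 1, with no new visits.
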